	
Secondary Analyses
 
At each sampling time point, the actual value and the change from baseline for α-Gal A, Gb3 and lyso-Gb3, eGFR, ejection fraction, global longitudinal strain, LVMI and left ventricular systolic function will be summarized by dose and cohort using descriptive statistics and plotted over the 1-year study period by dose and cohort. Similar summaries will also be provided for ERT naïve/ERT pseudo-naïve subjects, and separately for ERT subjects (migalastat subjects will be grouped with either the ERT naïve/ERT pseudo-naïve subjects, or with the ERT subject, based on the clinical response determined by the Investigator at Screening).
 
For subjects who undergo ERT withdrawal, changes from pre- to post- ERT withdrawal in the frequency and dose of ERT infusions will be evaluated and summarized using annualized total dose and number of infusions. Duration of ERT withdrawal may also be analyzed.
 
Clearance of ST-920 measured by vector genomes in the different samples (plasma, saliva, urine, stool, and semen, if applicable) will be summarized over time by dose and cohort.
 
Exploratory Analyses
 
Data permitting, the following exploratory endpoints and their change from baseline summaries by dose and cohort will be provided at each sampling time point over the 1-year study period:
 
 • LGE, native myocardial T1 values and T2 mapping measured by CMR • High-sensitivity troponin T, NT-proBNP and other cardiac biomarkers • MLHF-Q summary score • UPCR and UACR • Biomarkers of renal function in urine • Neuropathic pain measured by the BPI • Frequency of pain medication use • GI symptoms measured by the GI symptoms rating scale • MSSI • QOL patient-reported outcome measured by the SF-36 questionnaire • α-Gal A activity measured in skin • Gb3 inclusion levels measured in skin in ERT-naïve and ERT-pseudo-naïve subjects and selected subjects previously on migalastat • Gb3 and lyso-Gb3 levels in urine for all subjects over time • Pulmonary function over time • Audiologic function over time 
Data permitting, summaries of percent reduction from baseline at Week 24 by dose and cohort will be provided for:
 
 • Gb3 inclusion in the kidney (assessed by kidney biopsy) in ERT-naïve and ERT-pseudo-naïve subjects and selected subjects previously on migalastat 
Summaries by dose and cohort will be provided for the following exploratory endpoints at each sampling time point:
 
 • Measurement of antibodies to AAV2/6 • Assessment of cell-mediated immune response to AAV2/6 • Measurement of immune response to α-Gal A
--	--

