Inclusion & Exclusion Criteria	
Inclusion Criteria
 
 ≥ 18 years of age Signed, written informed consent Diagnosis of Fabry disease One or more of the following symptoms: i) cornea verticillata, ii) acroparesthesia, iii) anhidrosis, iv) angiokeratoma Subjects who are on ERT or are ERT-naïve or are ERT-pseudo-naïve (defined as not having received ERT treatment during the 6 months prior to baseline). For subjects receiving ERT, ERT must have been administered at a stable dose and regimen for at least 6 months (defined as not having missed more than 3 doses of ERT during the 6 months prior to consent). Subjects on migalastat (Galafold™) must agree to withdraw migalastat prior to Baseline and, if non-responder to migalastat (based on clinical and/or biochemical assessments), undergo an incisional skin biopsy and kidney biopsy. Male subjects must refrain from sperm donation from the time of ST-920 administration until a minimum of 3 consecutive semen samples are negative for AAV2/6 after administration of ST-920 and a minimum of 90 days after ST-920 administration. Female subjects must refrain from egg donation from the time of ST-920 administration until all the samples are negative for AAV2/6 after administration of ST-920. Subjects must agree to use a highly effective form of contraception from the time of ST-920 administration until a minimum of 90 days after ST-920 administration and, for male subjects, a minimum of 3 consecutive semen samples are negative for AAV2/6 after administration of ST-920. Highly effective birth control methods include: 
 a documented vasectomy or permanent sterilization 	

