--	---

	
16. Known hypersensitivity to components of ST-920 formulation
 
17. Any other reason that, in the opinion of the Site Investigator or Medical Monitor, would render the subject unsuitable for participation in the study, including but not limited to risk of COVID-19 infection
 
Additional exclusion criteria for:
 
Cohorts 1- 4, female and renal cohort:
 
18. Subjects who meet New York Heart Association (NYHA) Class III and IV
 
Renal cohort:
 
19. History of renal dialysis or transplantation
 
20. History of acute kidney insufficiency in the 6 months prior to screening
 
21. Angiotensin converting enzyme (ACE) inhibitor or angiotensin receptor blocker (ARB) therapy initiated within 4 weeks prior to screening or changed ACE inhibitor or ARB dose in the 4 weeks prior to screening
 
22. Urine protein to creatinine ratio (UPCR) > 0.5 g/g who are not being treated with an ACE inhibitor or ARB
 
Cardiac cohort:
 
23. Significant cardiac fibrosis defined as having more than 3 segments full thickness of late gadolinium enhancement on CMR
 
24. Any contraindications to CMR as per local hospital/institution guidelines
 
25. Angiotensin converting enzyme (ACE) inhibitor or angiotensin receptor blocker (ARB) therapy initiated within 4 weeks prior to screening or changed ACE inhibitor or ARB dose in the 4 weeks prior to screening
 
26. NYHA Class IV

Concomitant Medications	
All medications are permitted with limited exceptions. The use of potentially hepatotoxic agents including herbal supplements may be allowed based on discussion and agreement with the Medical Monitor.
 
For subjects receiving ERT, ERT must have been administered at a stable dose and regimen (defined as not having missed more than 3 doses of ERT during the 6 months prior to consent). Subjects should continue to receive ERT at a stable dose and regimen (14 days \pm 1 day) during the study as per standard of care unless they undergo ERT withdrawal.
 
Subjects who are ERT-naïve or ERT pseudo-naïve (defined as not having received ERT treatment in the 6 months prior to baseline) may not initiate treatment with ERT during the study period, unless dictated by clinical circumstances and following discussion with the Sponsor Medical Monitor. Subjects may not initiate treatment with migalastat (Galafold™) during the study period.

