For all dose escalation and expansion cohorts, subjects who received ERT prior to study participation will continue to receive ERT during the study and remain on their current dose and regimen per standard of care unless they undergo ERT withdrawal. For subjects on ERT, baseline testing of enzyme and substrate levels will be coordinated such that samples will be taken on 2 separate occasions in the morning at trough, defined as 14 days (\pm 1 day) after the previous ERT infusion. An additional time point will have been taken previously during the screening period, so as to have 3 time points to assess the residual activity of α -Gal A at trough prior to the gene therapy administration. These 3 samples must be taken at trough, and preferably at the same time during the day (e.g. in the morning) to minimize the potential impact of non-specific factors on enzyme activity.

Based on Sangamo's prior clinical experience with the AAV2/6 vector, an ALT elevation (suggestive of an immune reaction to the viral capsid) may be observed. Subjects will be closely monitored for ALT elevation throughout the study and the protocol-defined treatment (or treatment at the discretion of the Investigator and agreed upon with the Medical Monitor) with corticosteroids may be started in response to ALT elevation. Dose selection and guidance are provided in [Appendix 3](#) of the protocol.

For this Phase I/II study, the sample size of 2 subjects prior to a potential dose escalation was chosen based on:

- consideration of optimum benefit/risk of the one-time administration of ST-920 to subjects due to the known development of an immune response against AAV6, and hence inability to treat the same subject again with AAV6 if efficacy is not achieved
- recruitment feasibility in this orphan disease population, Fabry disease being a rare inherited X-linked metabolic disease:

- i) approximately 30-40% of subjects are expected to screen fail due to the presence of AAV6 neutralizing antibodies

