 - ii) only male subjects with classical Fabry disease will be recruited during dose escalation and, to ensure that any residual enzyme level does not interfere with the measurement of enzyme levels produced by the cDNA transgene, either ERT-naïve subjects or subjects on a stable dose and regimen (defined as not having missed more than 3 doses of ERT during the 6 months prior to consent) or ERT-pseudo-naïve subjects who have previously been on ERT but have not received ERT treatment during the 6 months prior to baseline, will be allowed in the study
- c) ability to detect any safety signal

This sample size of 2 subjects per cohort will provide a 28% chance of observing at least one AE for events with a $\geq 15\%$ incidence. In addition, for an expanded cohort of 6 subjects (2 + 4), the sample size of 6 subjects will provide a 62% chance of observing at least 1 AE for events with a $\geq 15\%$ incidence.

Safety and tolerability of ST-920 infusion in each cohort will be assessed by incidence of TEAEs and serious AEs (SAEs). Other safety assessments will include monitoring liver tests for any AAV-associated elevation of liver enzymes, clinical laboratory tests (chemistry, hematology, urinalysis), vital signs, AAV clearance from tissues including plasma, urine, saliva, stool and semen (if applicable). Safety data from 24 subjects treated in the Sponsor's studies with AAV2/6 have, to date, not identified any dose limiting safety concerns with treatment of subjects at the starting dose proposed in this study. Therefore, 2 subjects per dose during the escalation is believed appropriate to limit the number of subjects who may be exposed to a suboptimal dose, and to maximize treatment of subjects at the dose that will optimize the benefit risk assessment. This is particularly pertinent, considering that it is very unlikely that a subject could be retreated with this technology should they not experience efficacy at the dose tested.

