3.2 Screening Period

The objective of the screening visit is to identify subjects who meet the stated inclusion and exclusion criteria and who are willing and able to participate in the study. After informed consent, screening may take up to approximately 8 weeks and may be performed across several visits.

During screening, subjects will be assigned a subject number and will receive the screening assessments and procedures described in the Schedule of Events ([Appendix 1](#)). Subjects who complete all screening procedures, satisfy all eligibility criteria and have their eligibility packet verified by the site and approved by the Medical Monitor will be considered enrolled in the study.

Subjects may be re-screened for participation in the study at the judgment of the Site Investigator and after consultation with Sponsor. See the Schedule of Events ([Appendix 1](#)) for a list of assessments performed in the previous 6 months that may be used for evaluation of inclusion/exclusion criteria at the judgment of the Site Investigator. Genetic marker analysis including Fabry disease gene sequencing will not be repeated as this will not change over time. In addition, Fabry disease gene sequencing will only be performed at screening if no prior documented gene sequencing results are available. The genotyping will only be used to confirm that subjects have a mutation in the *GLA* gene. The diagnosis of classical Fabry disease will be made on the basis of enzyme activity and clinical symptoms for male subjects. For females the diagnosis will be made based on mutation and clinical symptoms.

A sample will be taken during the screening period to measure baseline levels of enzyme and substrate levels. Two more samples for baseline levels of enzyme and substrate will be taken during the baseline period (see [Section 3.3](#)), so as to have 3 time points to assess the residual activity of α -Gal A prior to the gene therapy administration. For subjects on ERT, testing of enzyme and substrate levels will be coordinated such that samples will be taken at trough, defined as 14 days (± 1 day) after the previous ERT administration, and preferably at the same time during the day (e.g. in the morning) to minimize the potential impact of non-specific factors on enzyme activity.

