4. SUBJECT SELECTION

4.1 Inclusion Criteria

1. ≥ 18 years of age
2. Signed, written informed consent
3. Diagnosis of Fabry disease
4. One or more of the following symptoms: i) cornea verticillata, ii) acroparesthesia, iii) anhidrosis, iv) angiokeratoma
5. Subjects who are on ERT or are ERT-naïve or are ERT-pseudo-naïve (defined as not having received ERT treatment in the 6 months prior to baseline). For subjects receiving ERT, ERT must have been administered at a stable dose and regimen for at least 6 months (defined as not having missed more than 3 doses of ERT during the 6 months prior to consent).
6. Subjects on migalastat (Galafold™) must agree to withdraw migalastat prior to Baseline and, if non-responder to migalastat (based on clinical and/or biochemical assessments), undergo an incisional skin biopsy and kidney biopsy.
7. Male subjects must refrain from sperm donation from the time of ST-920 administration until a minimum of 3 consecutive semen samples are negative for AAV2/6 after administration of ST-920 and a minimum of 90 days after ST-920 administration.
8. Female subjects must refrain from egg donation from the time of ST-920 administration until all the samples are negative for AAV2/6 after administration of ST-920.
9. Subjects must agree to use a highly effective form of contraception from the time of ST-920 administration until a minimum of minimum of 90 days after ST-920 administration and, for male subjects, 3 consecutive semen samples are negative for AAV2/6 after administration of ST-920. Highly effective birth control methods include:
 - i. a documented vasectomy or permanent sterilization
 - ii. condom
 - iii. combined (estrogen and progestogen containing) hormonal contraception (oral, intravaginal or transdermal)
 - iv. progestogen-only hormonal contraception associated with inhibition of ovulation (oral, injectable or implantable)
 - v. intrauterine device (IUD)
 - vi. intrauterine hormone-releasing system (IUS)

- vii. sexual abstinence is acceptable only as true abstinence and when in line with the preferred and usual lifestyle of the subject. Periodic abstinence (e.g. calendar, ovulation, symptothermal, post-ovulation methods) and withdrawal are not acceptable methods of contraception
- 10. Subject must be fully vaccinated (as per the Centers for Disease Control and Prevention (CDC) definition in the US and as per local guidelines in other countries) for COVID-19 at least one month prior to dosing

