6.1.8 ERT Administration Log

The frequency of ERT administration will be studied before and after administration of ST-920. Each dose of ERT given to the subject from the time of screening will be recorded on the ERT Administration Log, including date and time of start and stop of ERT infusion. At each indicated visit, documentation of all ERT administration since the last visit must be obtained and confirmed. An assumed standing schedule (e.g., every other week) should not be used.

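### The stable-ERT criterion counts only missed doses, so an eight-week ERT gap ending near consent qualifies and can inflate the Gb3 and lyso-Gb3 baseline of subjects on ERT

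*Combined protocol and SAP*

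**What the plan says.** Criterion 5 (Synopsis and Section 4.1) admits subjects on ERT if it was given at a "stable dose and regimen for at least 6 months (defined as not having missed more than 3 doses of ERT", with the misses counted over the 6 months before consent. The same missed-dose definition recurs in the Synopsis under Concomitant Medications, in Section 3.1 and in Section 7.2. In those three places the words requiring at least 6 months are absent, and the bracket supplies the only time window. Section 3.1 gives the purpose: "to ensure that any residual enzyme level does not interfere with the measurement of enzyme levels produced by the cDNA transgene".

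After entry, subjects "remain on their current dose and regimen per standard of care unless they undergo ERT withdrawal", and Section 7.2 sets the interval at 14 days, plus or minus 1 day.

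Three enzyme and substrate samples precede dosing. Section 3.2 says: "A sample will be taken during the screening period to measure baseline levels of enzyme and substrate levels". Two more follow in the baseline period (Section 3.3), at least 13 days apart (Appendix 1, note n). For subjects on ERT, each is drawn at trough, 14 days (plus or minus 1) after the previous infusion. Screening may take about 8 weeks. The baseline period is up to 12 weeks, or 24 if delayed by COVID-19.

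On exposure records, Section 6.1.8 says: "Each dose of ERT given to the subject from the time of screening will be recorded on the ERT Administration Log".

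Change from baseline in plasma Gb3 and lyso-Gb3 is a secondary endpoint (Section 2.1) and part of the stated basis for judging preliminary bioactivity and efficacy (Section 3.4). There is no control arm. Section 6.4.1 expects most subjects to be on ERT at baseline.

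**The concern.** The criterion's words promise a stable dose and regimen, but its definition is only a count of misses. It sets no limit on consecutive misses, no minimum time since the last miss, and no condition on product. The trough rule fixes the interval from the last infusion and does not look at the gap before it. If substrate rises during a gap and falls once regular infusions resume, a subject sampled soon after resumption has a baseline above the usual on-ERT level. The return to that level then appears as a post-dose fall.

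No control group would reveal this, and the cohorts are small: two subjects can be the basis for escalation, and each expansion cohort holds at most six. Substrate is also compared with baseline after ERT withdrawal (Section 3.6). An inflated baseline would exaggerate a fall there, or hide a rise.

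The protocol already uses this kind of control elsewhere. Exclusions 21 and 25 bar starting an ACE inhibitor or ARB, or changing its dose, in the 4 weeks before screening for the renal and cardiac cohorts. ERT acts directly on the substrate endpoint but has no comparably explicit rule.

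**Working it through.** The plan states no figure on this point, so there is none to reproduce.

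**Length of the permitted gap.** Inputs: 3 missed doses (criterion 5) and a 14-day interval, plus or minus 1 day (Section 7.2).

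- Gap = (missed doses + 1) x interval = 4 x 14 = 56 days, or 8.0 weeks. At 13- and 15-day intervals it is 52 and 60 days.
- Doses scheduled in 6 months: 182.5 / 14 = about 13. Three misses are 3/13 = 23% of them.

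**How much of a gap-related excess reaches baseline.** The documents give no substrate kinetics, so the following are assumptions:

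- At the end of the gap, trough lyso-Gb3 is 10% or 30% above the subject's regular-ERT level (excess x).
- The excess decays with a half-life of 1, 2, 4 or 8 weeks once ERT resumes.
- Baseline is the mean of the three samples. The supplied text gives no rule.
- The excess has gone by the post-dose visit, and ST-920 has no effect.

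Share of the excess left at t weeks after resumption = 0.5^(t / half-life). Two sampling patterns fit the protocol windows: early (2, 4 and 6 weeks) and late (8, 18 and 20 weeks). With s the mean share over the three samples, rounded to a whole percent, the spurious change from baseline = 1 / (1 + s·x) - 1.

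| Half-life (weeks) | Early: s | x = 10% | x = 30% | Late: s | x = 10% | x = 30% |
|---|---|---|---|---|---|---|
| 1 | 11% | -1.1% | -3.2% | 0% | 0.0% | 0.0% |
| 2 | 29% | -2.8% | -8.0% | 2% | -0.2% | -0.6% |
| 4 | 52% | -4.9% | -13.5% | 11% | -1.1% | -3.2% |
| 8 | 71% | -6.6% | -17.6% | 30% | -2.9% | -8.3% |

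For the extreme cell: 0.71 x 0.30 = 0.213, and 1 / 1.213 - 1 = -17.6%.

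**Effect on a small group.** One subject at -17.6%, with the others unaffected, moves the mean percent change by -17.6 / 2 = -8.8 points in a group of two and by -17.6 / 6 = -2.9 points in a group of six.

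**The case against.** The strongest reply is that the criterion's own words do more than its bracket. On a plain reading, a stable dose and regimen for at least 6 months excludes a dose raised a week before consent, and the Medical Monitor approves each eligibility packet (Sections 3.2 and 3.4). This stands. A reader might infer that a recent dose increase clearly qualifies, but the documents support only an ambiguity. The points about product and consecutive misses do not depend on that reading.

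Second, safeguards exist: three trough samples, on-study ERT every 14 days, a dose log from screening, and up to 20 weeks of screening and baseline. They reduce carry-over, as the late-sampling columns show. They do not exclude it, because those periods are maxima and early sampling is allowed.

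Third, summaries are descriptive, and ERT subjects are shown separately from naïve and pseudo-naïve subjects (Section 11.2.3). A reader might infer that the plan credits any substrate fall to ST-920. No section does so. Even so, a descriptive mean change carries the bias of its baseline. After complete ERT withdrawal, ongoing ERT cannot explain a sustained fall, although an inflated baseline would still overstate its size.

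Fourth, sites take a medical history including concomitant medications (Section 6.1.1), and criterion 5 cannot be applied without past infusion dates. The information will therefore be seen, but the dose-by-dose log starts at screening. Section 11.2 defers details to an SAP, which may define baseline; the supplied text does not.

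**Conclusion.** The point holds as a weakness in eligibility wording and baseline sampling for subjects on ERT. A 56-day gap ending near consent satisfies the only operational definition of stable ERT, and no rule requires regular infusions before the baseline samples. Part of a later fall in Gb3 or lyso-Gb3 can then reflect resumed ERT. Naïve and pseudo-naïve subjects are not affected.

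The size cannot be computed from the documents. Under the stated assumptions it runs from about 0% (late sampling or fast decay) to about -18% (early sampling, 30% excess, 8-week half-life). A reader might take 1 / 1.30 - 1 = -23% as the limit for a 30% excess. That needs the full excess, undiminished, in all three samples and then its complete disappearance after dosing. Every trough sample comes about 14 days after an infusion, so some decay is expected.

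A reader might also infer that the error always favours ST-920. It does after a gap, but if the criterion does admit recent dose changes, a recent reduction could bias the other way. How many subjects would be affected is unknown.

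**What to change.** 1. **Criterion 5 and its repeats** (Synopsis, Sections 3.1, 4.1 and 7.2): the sponsor should reconcile the requirement with its bracket, stating whether product, dose and interval must all be unchanged over the 6 months and how consecutive misses are treated.
2. **Sections 3.2 and 3.3**: take the enzyme and substrate samples that form the baseline only after a sponsor-specified run of on-time infusions, within the existing screening and baseline windows. State how the three samples form the baseline value.
3. **Data and analysis** (Sections 6.1.8 and 11.2.3): record ERT product, dose and infusion dates for the 6 months before consent. Repeat the ERT-subject substrate summaries without subjects who had a recent gap or change, pooling across cohorts where cells are small.

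The cost is that a few baseline draws move later, one history item is added to the CRF (from records that sites must already review for criterion 5), and one extra descriptive table is produced.
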